13.3.1.2 Dilated Funduscopic Exam

The result from the optic nerve exam, vitreous exam, macula exam and peripheral retina exam will be summarized using counts and percentages of Normal, Abnormal NCS and Abnormal CS and will be presented by eye and time point.

13.3.2 Optos Photography

Optos photography includes a widefield dilated Optos photograph of the posterior segment with any cell cluster from the anterior vitreous visualized in the photo frame along with the posterior segment/fundus. Two directions of gaze are captured to best potentially visualize jCell.

For Optos photography, results will be included in data listings only.

13.3.3 Intraocular Pressure

The change in IOP from baseline will be summarized descriptively for each time point.

13.3.4 Clinical Vitreous Exam

For the clinical vitreous exam, counts and percentages will be summarized for method used (Indirect Ophthalmoscopy, Slit Lamp Exam, Other), whether jCell is visualized, the predominant

shape of the jCell (Sphere/Ellipsoid, Strand(s), Diffuse Haze no opacities >2DD, Debris or Graft Remnants and Other), the estimated location of jCell in the vitreous (e.g. anterior 1/3).

Other details collected for the clinical vitreous exam will be provided in a data listing, including date of examination, the secondary shape of the jCell aggregate, size on the horizontal axis, and size on the vertical axis.

13.3.5 Optical Coherence Tomography (OCT)

OCT results will be summarized in a table showing the counts and percentages of subjects whose eyes (both Study Eye and Non-Study Eye) show cystoid macular edema (CME) present, and of those who show CME, how many cases involve the foveal center; epiretinal membrane formation present and how many have evidence of retinal traction present. In addition, investigator observations of ellipsoid zone (EZ) presence will be summarized as Not Present; Present but Reduced; Present and Near Normal.

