6.3.7 End of Treatment (Month 12) or Early Termination Visit +/- 10 days

Performed at clinical study site 12 months post-treatment

- a. MH and physical exam, including weight and height
- b. vital signs
- c. pregnancy test (if applicable)
- d. CBC, platelet, differential, hemoglobin, hematocrit
- e. blood chemistries, not limited to, but must include AP, ALT, AST, BUN, Cr, total bilirubin, serum electrolytes, glucose, calcium, phosphate, albumin and total protein
- f. urinalysis
- g. slit lamp and fundus exam
- h. Optos photography
- i. BCVA
- j. IOP
- k. OCT (performed at site and sent to central reading lab for analysis)
- l. con meds
- m. adverse events

Performed at jCyte low vision facility 12 months post-treatment

- n. VF
- o. Contrast Sensitivity
- p. Mobility test
- q. optional exploratory ophthalmic imaging: ultrasound imaging (UBM, A- and Bscan), additional variants of slit lamp biomicroscopy with photography/videography using gonioscopy lens, OCT of jCells and/or retinal sensitivity with FST.

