7.2.2 Spectral Domain Optical Coherence Tomography (OCT) (performed locally and read centrally)

A clinical OCT machine will be used for data collection; the same machine should be used for any given patient at each time point. OCT results will be sent to a central reading lab for assessment.

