13.4 Clinical Laboratory Evaluation

Hematology and Chemistry laboratory parameters will be summarized using descriptive statistics at Baseline, Day 28, Month 3, Month 6, and Month 12. Change from baseline in the laboratory parameters will also be presented, with the baseline value defined as the last non-missing value recorded prior to the date and time of study drug administration.

Urinalysis assessments will be done at Screening, Baseline, Month 3, Month 6, and Month 12 or Early Termination and results will not be summarized but will be provided in a data listing.

Blood samples for testing for PRA and DRA will be taken at Baseline, Day 28 and Month 6 and results will be provided as a separate listing (not from the clinical database).

Coagulation tests will be done at Screening and results will be provided in a data listing.

Pregnancy test results will be provided in a data listing.

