15. CHANGES TO PROTOCOL-SPECIFIED ANALYSES

The study protocol lists mobility (maze) as a secondary objective. The name of this test has since changed to Low Luminance Mobility Test and this name is used throughout this analysis plan. Additionally, the study protocol lists A-scan ultrasound as an exploratory assessment. However, this assessment was not included in the final list of study assessments and was not performed on any patients.

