14.3.3.5	Intraocular Pressure (IOP): Study Eye	Safety Population	
14.3.3.6	Intraocular Pressure (IOP): Non-Study Eye	Safety Population	
14.3.3.7	Clinical Vitreous Exam: Study Eye	Safety Population	
14.3.3.8	Categorical Analysis of Optical Coherence Tomography (OCT)	Safety Population	
14.3.4	Other Safety Data		
14.3.4.1	Hematology	Safety Population	
14.3.4.2	Chemistry	Safety Population	
14.3.4.3	Vital Signs	Safety Population	· · · · · · · · · · · · · · · · · · ·

Abbreviations: ECG=electrocardiogram; E-ETDRS= electronic visual acuity testing algorithm; FA=full analysis; ICH=International Council for Harmonisation of Technical Requirements for Pharmaceuticals for Human Use; PP=per-protocol; TEAE=treatment-mergent adverse events

Index of Sectior	ı 16.2		
ICH Listing Number	Listing Title	Analysis Set	Comments
16.2	Subject Data Listings		
16.2.1	Discontinued Subjects		
16.2.1.1	Subject Disposition	All Subjects	
16.2.2	Protocol Deviations		
16.2.2.1	Protocol Deviations	All Subjects	
16.2.3	Demographic Data		
16.2.3.1	Demographics and Baseline Characteristics	Safety Population	
16.2.3.2	Medical History	Safety Population	
16.2.3.3	Ocular Medical History	Safety Population	
16.2.3.4	Prior and Concomitant Medications	Safety Population	
16.2.4	Individual Efficacy Response Data		
16.2.4.1.1	Best Corrected Visual Acuity (E-ETDRS): Study Eye	Safety Population	
16.2.4.1.2	Best Corrected Visual Acuity (E-ETDRS): Non-Study Eye	Safety Population	
16.2.4.2.1	Low Luminance Mobility Test (LLMT): Study Eye	Safety Population	
16.2.4.2.2	Low Luminance Mobility Test (LLMT): Both Eyes	Safety Population	
16.2.4.3.1	Kinetic Visual Fields (KVF): Study Eye	Safety Population	
16.2.4.3.2	Kinetic Visual Fields (KVF): Non-Study Eye	Safety Population	
16.2.4.4.1	Contrast Sensitivity Test (CST): Study Eye	Safety Population	
16.2.4.4.2	Contrast Sensitivity Test (CST): Non-Study Eye	Safety Population	
16.2.5	Compliance and/or Drug Concentration Data		
16.2.5.1	Study Drug Administration	Safety Population	
16.2.6	Adverse Events		
16.2.6.1	Adverse Events	Safety Population	
16.2.6.2	Serious Adverse Events	Safety Population	
16.2.6.3	Related Adverse Events	Safety Population	
16.2.7	Ophthalmic Safety Examinations		
16.2.7.1.1	Slit Lamp Exam: Study Eye	Safety Population	
16.2.7.1.2	Slit Lamp Exam: Study Eye -Vitreous Findings	Safety Population	

CONFIDENTIAL

Page 28/32

Statistical Analysis Plan 09 Nov 2022

jCyte, Inc Protocol No. JC02-2

S
4
3

jCyte, Inc Protocol No. JC02-2

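### SAP 13.3.5 tabulates the investigator's ellipsoid-zone grade although the protocol has the scheduled clinical OCT read by a central lab, and the SAP neither plans an output identified as central reads nor declares the change

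*SAP*

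**What the plan says.** **Protocol.** Section 7.2.2 states in its heading that the OCT is done locally and read centrally, and its text adds: "OCT results will be sent to a central reading lab for assessment". The visit lists agree. Section 6.2 (Baseline) and section 6.3.7 (Month 12 or early termination) both carry the item "OCT (performed at site and sent to central reading lab for analysis". Table 2 schedules the OCT at those two visits only.

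**SAP.** Section 13.3.5 has two parts. The first begins "OCT results will be summarized in a table showing the counts and percentages of subjects whose eyes" and covers cystoid macular edema, involvement of the foveal center, epiretinal membrane and retinal traction, in study and non-study eyes. It names no reader. The second part adds the EZ and does name one: "investigator observations of ellipsoid zone (EZ) presence will be summarized", in three levels that run from absent to near normal.

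Appendix B plans one clinical OCT table, 14.3.3.8, titled "Categorical Analysis of Optical Coherence Tomography (OCT", and one clinical OCT listing, 16.2.7.7. Neither title mentions central reads. Section 15, which records changes to the protocol's analyses, covers the renamed mobility test and one further item: "Additionally, the study protocol lists A-scan ultrasound as an exploratory assessment". The OCT reader is not there.

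**The concern.** The protocol and the SAP name different readers for the same image. For the EZ this is an explicit rule in the SAP that departs from the protocol, so it is more than a missing detail.

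The design makes the choice of reader matter. The study is single-arm, lists three centers in the synopsis, and has the investigator give the injection (Protocol 5.2). No masking of the investigator is described. Someone who knows which eye was re-injected, and that the image is from Month 12, can let that knowledge influence a three-level grade. Protocol 9.2 makes the injected eye's own baseline its control for visual parameters, and there is no untreated arm. A drift in grading between baseline and Month 12 would therefore look like a change in the eye. Sites may also place the boundary between reduced and near-normal EZ differently. One reading lab removes that between-site difference.

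Two things are at stake. Edema, membrane and traction are reported as ocular safety findings in a study whose primary objective is the safety of re-injection, and a reader of the table could not tell who graded them. The EZ also has a role in the program: Protocol section 1, in the rationale for the study, says baseline EZ thickness on OCT may predict who benefits.

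**Working it through.** There is no figure in the plan to reproduce, so the check is a comparison of the two documents, variable by variable.

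| OCT variable in SAP 13.3.5 | Reader under the protocol (6.2, 6.3.7, 7.2.2) | Reader under SAP 13.3.5 |
|---|---|---|
| Cystoid macular edema present | Central lab | Not named |
| Edema involves foveal center | Central lab | Not named |
| Epiretinal membrane present | Central lab | Not named |
| Retinal traction present | Central lab | Not named |
| EZ presence, three levels | Central lab | Investigator |

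The protocol column reflects the rule that OCT results go to the central lab. The protocol does not list which variables the lab returns.

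1. **Tally.** Of five variables, one is assigned to a different reader, four are unassigned, and none is assigned to the central lab.

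2. **How many readings are involved.** With 25 to 30 subjects, two eyes (the SAP reports both) and two scheduled visits, the upper limit is 25 × 2 × 2 = 100 to 30 × 2 × 2 = 120 eye-visits. This assumes both eyes are imaged and no visit is missed. For study eyes alone it is 25 × 2 = 50 to 30 × 2 = 60.

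3. **Is it shorthand?** The SAP does flag results from outside the clinical database in another place. For the PRA and DRA antibody tests, section 13.4 says: "results will be provided as a separate listing (not from the clinical database". There is no similar statement for central OCT reads.

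4. **Is the change declared elsewhere?** Section 15 is the place for it and is silent. The SAP text and output index that can be read do not mention a central OCT reading lab.

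5. **Can it be repaired later?** SAP section 6 treats any analysis done after database lock as post hoc and exploratory. If central reads are not placed in the plan before lock, tabulating them afterwards would carry that label, although the protocol required the readings.

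6. **What depends on it?** OCT is not among the efficacy endpoints (Protocol 3.2.1, SAP 10.1.1) or the main safety criteria (Protocol 3.2.2). SAP 13.3.5 gives counts and percentages. No hypothesis test or sample-size argument uses it.

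**The case against.** The strongest reply is that SAP 13.3.5 can be read as adding an investigator item to results that are otherwise centrally read. The first part speaks of OCT results in general, and the EZ sentence follows as an addition. Output titles in Appendix B do not normally name the data source: the mobility tables do not mention their masked graders. The eCRF and the study procedure manual, which might settle the source, are cited but are not among the documents, and the Appendix D table layouts are not available to read. This stands for edema, foveal involvement, membrane and traction, where the source is unstated and not shown to be local. It does not help the EZ: on that reading too, the EZ is tabulated from the investigator and no central EZ result is planned.

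The consequence is also modest, and that stands. The output is descriptive, no subgroup analysis is planned (SAP 10.5), and the program's interest is in baseline EZ thickness while the SAP grades presence. Ocular harms have other routes into the report, through the adverse event tables and the funduscopic examination. A baseline grade recorded before the injection cannot be influenced by what follows it.

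A reader might go further in four ways that the documents do not support:

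- **That all OCT is centrally read.** Central reading is stated for the scheduled clinical OCT only. The optional OCT of the injected cells at the sponsor's facility has no such rule.
- **That the investigator's grade is the poorer one, or that the central reader is masked.** There are no agreement or reliability data. Masked graders are stated for the mobility test only. The investigator's lack of masking is itself an inference from the design.
- **That central readings will be collected and left unreported.** For four variables the table may already use them, and the documents do not say what the lab returns.
- **That a certain number of eyes would change category.** No agreement rate is given, so any count would rest on an invented rate.

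**Conclusion.** The point holds as an undeclared mismatch over who reads the OCT. For the EZ, the SAP states a rule that differs from the protocol. For the other four variables it leaves the reader open. In neither case does it plan an output identified as central reads.

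The mismatch covers up to 100 to 120 eye-visits in one descriptive table and one listing. No endpoint, test or sample size is affected. The direction and size of any grading bias cannot be estimated from the documents.

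The conclusion rests on two assumptions: that investigators know the treated eye and the visit, which the single-arm design and their role in giving the injection make reasonable, and that the lab returns at least some of the tabulated variables. If it returns no EZ grade, an investigator grade may be the only one available, but the SAP should then say so. The change is worth making because the protocol already requires the central reading.

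**What to change.** In SAP 13.3.5:

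- Base Table 14.3.3.8 and Listing 16.2.7.7 on the central reading lab's result for the EZ and for every other OCT variable the lab returns.
- Show the investigator's reading beside the central one in the listing.
- Name the reader for each variable.
- Label any variable the lab does not return as investigator-read, and declare this in section 15.

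The sponsor should first confirm which variables the lab returns. The cost is SAP wording, a data transfer and one extra listing column. No added patient procedure is needed. The work should be settled before database lock so that the central reads count as planned output.

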13.4 Clinical Laboratory Evaluation

Hematology and Chemistry laboratory parameters will be summarized using descriptive statistics at Baseline, Day 28, Month 3, Month 6, and Month 12. Change from baseline in the laboratory parameters will also be presented, with the baseline value defined as the last non-missing value recorded prior to the date and time of study drug administration.

Urinalysis assessments will be done at Screening, Baseline, Month 3, Month 6, and Month 12 or Early Termination and results will not be summarized but will be provided in a data listing.

Blood samples for testing for PRA and DRA will be taken at Baseline, Day 28 and Month 6 and results will be provided as a separate listing (not from the clinical database).

Coagulation tests will be done at Screening and results will be provided in a data listing.

Pregnancy test results will be provided in a data listing.

13.5 Vital Signs

Vital signs (including temperature, heart rate, respiration rate, systolic blood pressure (BP) and diastolic BP) will be summarized using descriptive statistics at Baseline and at each post-baseline time point. Changes from baseline will also be summarized. The baseline value is defined as the last non-missing value recorded prior to the date and time of study drug administration.

13.6 Physical Examination

Physical examination results will be included in data listings only.

14. OTHER DATA

14.1 Procedures

Details of any non-study procedures that occurred during the study will be collected on the eCRF. Details collected will include the type and date of procedure and whether the procedure was conducted due to a medical history, ocular history, adverse event or other indication.

Procedures will be provided in data listings only.

15. CHANGES TO PROTOCOL-SPECIFIED ANALYSES

The study protocol lists mobility (maze) as a secondary objective. The name of this test has since changed to Low Luminance Mobility Test and this name is used throughout this analysis plan. Additionally, the study protocol lists A-scan ultrasound as an exploratory assessment. However, this assessment was not included in the final list of study assessments and was not performed on any patients.

17. APPENDICES

APPENDIX A: PRESENTATION OF DATA AND PROGRAMMING SPECIFICATIONS

General

- Specialized text styles, such as bold, italics, borders, shading, and superscripted and subscripted text will not be used in tables, figures, and data listings (TFLs) unless they add significant value to the TFL.
- Only standard keyboard characters are to be used in tables and data listings.
- Special characters, such as nonprintable control characters and printer- or font-specific characters, will not be used in a TFL.
- Hexadecimal character representations are allowed (e.g., μ , α , and β).
- All footnotes will be left justified and at the bottom of a page. Footnotes must be used sparingly and add value to the TFL.

Tables

- Means and medians will be presented to one decimal place more than the raw data. Standard deviations will be presented to two decimal places more than the raw data. Minimums and maximums will be reported with the same number of decimal places as the raw data.
- Percentages will be presented to the tenths place.
- For frequency counts of categorical variables, categories whose counts are zero will be displayed for the sake of completeness. For example, if none of the subjects discontinue due to "lost to follow-up," this reason will be included in the table with a count of zero. Categories with zero counts will not have zero percentages displayed.
- Lower and upper CI values must be presented to one decimal place more than the raw/derived data (i.e., to the same number of decimal places as the mean).
- Percentiles (e.g., 25% and 75%) must be presented to one decimal place more than the raw/derived data.
- For all inferential analyses, *P* values will be rounded to four decimal places (or at the highest level of precision) with a leading zero (0.0001). *P* values less than 0.0001 will be presented as "<0.0001."
- The last footnotes will be:
 - "Source: xxx", where xxx indicates the source table number(s), if applicable (in case aggregated results, such as the mean or median, are plotted), source listing(s) (in case individual responses are plotted), and/or source dataset(s) (e.g., ADaM).
 - "PROGRAM SOURCE:...\\xx.sas, DATA CUTOFF DATE: DD Mmm YYYY, RUN DATE: DD Mmm YYYY hh:mm".

Listings

- If not otherwise specified, all data listings will be sorted by center, subject number, visit, and date/time, as appropriate.
- All date values will be presented in an ISO8601 date (e.g., 2018-10-11) format.
- All observed time values will be presented using a 24-hour clock HH:MM:SS format (e.g., 01:35:45 or 11:26). Seconds will only be reported if they were measured as part of the study.
- The last footnote will be "PROGRAM SOURCE:...\xx.sas, DATA CUTOFF DATE: DD Mmm YYYY, RUN DATE: DD Mmm YYYY hh:mm".

Missing or Incomplete Dates (i.e., Adverse Events and Concomitant Medications)

The most conservative approach will be systematically considered. If the adverse event (AE) onset date is missing/incomplete, it is assumed to have occurred during the study treatment phase (i.e., considered a treatment-emergent AE) except if the partial onset date or other data, such as the stop date, indicates differently. Similarly, a medication with partial start and stop dates could be considered as both a prior and concomitant medication.

The following algorithms will be applied to missing and incomplete start and stop dates:

Start Dates

- If the day portion of the start date is missing, then the start date will be estimated to be equal to the date of the first dose of study drug, provided the start month and year are the same as the date of the first dose of study drug and stop date is either after the date of the first dose of study drug or completely missing. Otherwise, the missing day portion will be estimated as "01."
- If both the day and month portions of the start date are missing, then the start date will be estimated to be equal to the date of the first dose of study drug, provided the start year is the same as the date of the first dose of study drug and stop date is either after the date of the first dose of study drug or completely missing. Otherwise, the event will be assumed to start on the first day of the given year (e.g. ??-???-2013 is estimated as 01-JAN-2013).
- If the start date is completely missing and stop date is either after the date of the study drug administration or completely missing, then the start date will be estimated to be equal to the date of study drug dosing. Otherwise, the start date will be estimated to be the first day of the same year as the stop date.

All other non-AE and non-concomitant medication day calculations where only partial dates are available will be handled as follows: the first day of the month will be used in the calculations if the day part of a start date is missing, and January 1 will be used if both the month and day parts of a start date are missing.

jCyte, Inc Protocol No. JC02-2

Stop Dates

- If only the day of resolution is unknown, the day of resolution of the event will be assumed to be the last day of the month (e.g. ??-JAN-2013 will be treated as 31-JAN-2013).
- If both the day and month of resolution are unknown, the day of resolution of the event will be assumed to be the last day of the year (e.g. ??-??-2013 will be treated as 31-DEC-2013).
- If the stop date of the event is completely missing or event is continuing, the event resolution will be assumed to be after the first dose of study drug, and the stop date will be imputed using the last known date on the study.

Standard Calculations

Variables requiring calculation will be derived using the following formulas:

- Days: A duration expressed in days between one date (date1) and another later date (date2) is calculated using the following formula: duration in days = date2 date1 + 1
- Months: A duration expressed in months is calculated using the INTCK function of SAS using the following formula: months = intck('month', 'date1'd, date2'd, 'continuous')
- Years: A duration expressed in years between one date (date1) and another later date (date2) is calculated using the following formula: duration in years = intck('year', 'date1'd, 'date2'd, 'continuous')
- Height: Height entries made in inches are converted to centimeters using the following formula: height (cm) = height (in) × 2.54
- Weight: Weight entries made in pounds are converted to kilograms using the following formula: weight (kg) = weight (lb)/2.2046
- Temperature: Temperature entries in degrees Fahrenheit are converted to degrees centigrade using the following formula: temperature ($^{\circ}C$) = 5/9 × [temperature ($^{\circ}F$) 32]
- Body Mass Index (BMI): BMI is calculated using height and weight using and is calculated using the following formula: BMI (kg/m²) = weight (kg)/[[height (cm)/100]²]
- Change from baseline: Change from baseline will be calculated using the following formula: change = post-baseline value – baseline value
- Percent change from baseline: Percent change from baseline will be calculated using the following formula: percent change from baseline = (post-baseline value baseline value)/baseline value × 100.

S
<  
P P
D
\circ
_

Statistical Analysis Plan 09 Nov 2022

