13.2 Adverse Events

All AE summaries will be restricted to treatment-emergent AEs (TEAEs), which are defined as those AEs that occurred after dosing and those existing AEs that worsened during the study. In the case of worsening in severity, a new entry is created in the database with start date equal to start of worsening. If it cannot be determined whether the AE is treatment-emergent due to a partial onset date, then it will be counted as such. Verbatim terms in the eCRFs will be mapped to SOCs and PTs using MedDRA, version 23.1.

AE summaries that are displayed by SOC and PTs will be ordered by descending subject count by SOC and PT within SOC. Summaries of the following types will be presented:

- Overall summary of TEAEs that contains a summary of the following:
 - Subject and event count of any TEAE
 - Subject and event count of TEAEs related to study drug
 - Subject and event count of serious TEAEs
 - Subject and event count of any serious TEAE related to study drug
 - Subject and event count of severe TEAEs related to study drug

Separate TEAE summary tables will be provided as follows:

- Subject incidence and event count of TEAEs by MedDRA SOC and PT.
- Subject incidence and event count of TEAEs by MedDRA SOC, PT, and highest severity. At each level of subject summarization, a subject is classified according to the highest severity if the subject reported more than one of the same event. Categories of severity will be "Mild", "Moderate", "Severe" and "Life threatening". Adverse events with missing severity will be assigned to "Severe" for this summary.
- Subject incidence and event count of TEAEs related to study drug by MedDRA SOC and PT. Related AEs are those reported as "Related" and "Possibly Related". At each level of subject summarization, a subject is classified according to the closest relationship if the subject reported more than one of the same event. Adverse events with a missing relationship will be considered related for this summary.
- Subject incidence and event count of serious TEAEs by MedDRA SOC and PT.

Separate listings of related TEAEs and SAEs will be provided.

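### SAP Appendix A imputes an incompletely dated AE that stops on injection day to a date before injection, which conflicts with the rule in SAP 13.2 that undetermined cases count as treatment-emergent

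*SAP*

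**What the plan says.** SAP 13.2 limits the AE summaries to TEAEs, "which are defined as those AEs that occurred after dosing and those existing AEs that worsened during the study". It then deals with incomplete onset: "If it cannot be determined whether the AE is treatment-emergent due to a partial onset date, then it will be counted as such".

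The part of SAP Appendix A on missing or incomplete dates opens with the same intention: "The most conservative approach will be systematically considered". An event with a missing or incomplete onset is presumed treatment-emergent, "except if the partial onset date or other data, such as the stop date, indicates differently".

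Three start-date rules follow. Each uses the dosing date as onset only if the stop date is later than dosing or is wholly missing. The first two also require the known part of the onset to match the dosing month and year, or the dosing year. The fallbacks are:

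- Day missing: "stop date is either after the date of the first dose of study drug or completely missing. Otherwise, the missing day portion will be" set to 01.
- Day and month missing: "Otherwise, the event will be assumed to start on the first day of the given year".
- Onset wholly missing: "Otherwise, the start date will be estimated to be the first day of the same year as the stop date".

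**The concern.** The three rules leave out one boundary case, a stop date equal to the injection date. Such a stop date does not show that the event began before injection, because the event may equally have begun and ended in the hours after it. On the wording of 13.2 and of the opening of Appendix A, this is an undetermined case and should count as treatment-emergent. The rules instead give it a date before dosing.

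Safety is the primary objective and every AE table is confined to TEAEs, so the flag decides whether an event is tabulated. AEs are recorded from informed consent onward (protocol 8.1), so a pre-injection category exists into which such an event could fall.

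**Working it through.** The documents state no figure on this point, so this is a check of logic.

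**Inputs.** The three start-date rules and their fallbacks (SAP Appendix A), the TEAE definition and the partial-onset rule (SAP 13.2), and 25 to 30 subjects (SAP Section 5). The injection date of 15 March 2021 is an assumption for illustration. Where part of the onset is known, it matches the injection month and year, or year.

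**Step 1. Apply the rules literally.** Onset = injection date if stop > injection date or stop is missing. Otherwise onset = the fallback date.

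| Missing from onset | Stop 14 March | Stop 15 March | Stop 16 March | Stop missing |
|---|---|---|---|---|
| Day | 1 March | **1 March** | 15 March | 15 March |
| Day and month | 1 January | **1 January** | 15 March | 15 March |
| Everything | 1 January | **1 January** | 15 March | 15 March |

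The 14 March column is correct, since that event was over before injection. The 15 March column is the gap.

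**Step 2. See how general it is.** Take every injection date in a 365-day year, with the stop date equal to the injection date.

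- Day missing: the imputed onset precedes injection on 365 − 12 = 353 dates. The exceptions are the 12 firsts of the month.
- Day and month missing: 365 − 1 = 364 dates. The exception is 1 January.
- Everything missing: 365 − 1 = 364 dates, with the same exception.

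**Step 3. Change the condition to stop ≥ injection date.** The counts become 0, 0 and 0 of 365. The 15 March column then reads 15 March in all three rows, and the 14 March column does not change.

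**Step 4. Incomplete stop dates.** A stop date with a missing day is moved to the end of its month, and one with day and month missing to 31 December. These fall after injection unless injection was on that last day. The gap therefore mainly concerns known stop dates.

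**Step 5. Size of one event.** For a subject with no other TEAE of that term, one misclassified event changes subject incidence by 1/30 = 3.3 to 1/25 = 4.0 percentage points.

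**The case against.** The strongest reply is that nothing in the SAP derives the AE flag from the imputed date. SAP 9.5 ties imputed dates to classification for medications, but no sentence does so for AEs. A programmer who applied 13.2 directly would keep the event in. This stands, and it makes the consequence conditional. It does not remove the conflict: Appendix A says its algorithms will be applied to incomplete AE dates, Appendix B lists no table of AE duration or time to onset, and the SAP does not say which text prevails.

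The second reply is that the case should hardly arise. Date and time of onset are collected (protocol 8.1), subjects are observed for 60 minutes (protocol 5.1), and AEs are recorded on Day 0 and again on Day 1. This also stands. A reader might infer that injection-day pain, redness or pressure rise is likely to be lost. The documents do not support that, since these are the events least likely to lack an onset date.

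Third, a reader might infer that the error always favours the product. That would hold only if every such event began after injection. For an event that began between consent and injection and ended that day, the fallback classifies correctly.

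Fourth, a reader might cite the *on or after* wording in SAP 9.5 as proof of the intended boundary. That wording concerns whether medication use overlaps dosing, whereas TEAE status depends on onset or worsening after dosing. The comparison carries no weight here.

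Finally, the information is not lost. The event remains in Listing 16.2.6.1, and Table 14.3.1.1 reports whether AEs were observed at administration and the post-injection IOP.

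**Conclusion.** The point holds as a conflict between two parts of the SAP. For an AE with an incomplete onset that could include injection day and a stop date on injection day, the Appendix A rules give an onset before injection, apart from the calendar exceptions in the check. SAP 13.2 covers a partial onset of this kind and the opening of Appendix A also covers a wholly missing one; both would count the event as treatment-emergent.

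Exclusion from Tables 14.3.2.1 to 14.3.2.5 is possible but not certain, because it depends on the flag being derived from the imputed date. The documents do not support the firmer statement that the plan removes these events from the safety tables. Nor do they give any basis for estimating how many such events there would be. The 3.3 to 4.0 points describe a single hypothetical event and are not an expected bias. No formal test depends on the result, so this is a minor correction to the primary safety tabulation.

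**What to change.** In the three start-date rules of Appendix A, replace *after* with *on or after* the date of study drug administration, and treat an onset imputed to that date as treatment-emergent. Alternatively, add one sentence saying that the 13.2 rule overrides the imputed date. If the SAP can no longer be amended, record the handling in the clinical study report, as SAP Section 1 requires for deviations.

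The cost is one phrase in three rules and the matching program condition. The downside is that an event that began before injection and ended that day may be counted as a TEAE. That is the conservative direction the SAP has already chosen.
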